Duration of treatment	
Treatment duration for each patient will be variable.
 
For roll-over patients: at least 3 years; or until alternative treatment options become or are made available (e.g., via marketing authorization, via compassionate use, or via similar process) to the patient outside of the clinical trial.
 
For new patients: until the overall end of the trial (with expected minimum treatment duration of 76 weeks).
 
Exception: patients aged 21 years must complete the trial before their 22nd birthday. Consequently, a treatment duration of at least 3 years might not be reached by some patients aged 21.
 
The overall end of trial will take place approximately when last roll-over patient is expected to reach 3 years of treatment (██████████) ensuring that nintedanib or alternative treatment options (e.g., via marketing authorization, via compassionate use, or via similar process) will be available for all remaining patients (roll-over or new patients) outside the trial at this time.

Statistical methods	
Descriptive statistics will be provided for adverse events (██████████).

FLOW CHART V1-V11

Trial Periods	Screening	Treatment ³																		
Visits	1 ¹	2	3 ⁴	3a ^{3&4}	4	4a ³	5	5a ³	6	6a ³	7	7a ³	8	8a ³	9	9a ³	10	10a ³	11	11a ³
Weeks ²	-4		2		12		24		36		52		64		76		88		104	
Days ²	≤28d before D1	D1 ²	15		85		169		253		365		449		533		617		729	
Time window for visits (days)		none	±3		±3		±3		±7		±7		±7		±7		±7		±7	
Informed consent and assent ⁵	X																			
HRCT sent to central review ⁶	X																			
Biopsy sent to central review ⁷	X																			
Demographics	X																			
Medical history	X																			
Baseline conditions ⁸	X																			
██████████	X ³⁰																			
Physical examination, Vital signs ⁹	X	X	X		X		X		X		X		X		X		X		X	
Height (standing and sitting) ¹⁰	X	X			X		X		X		X		X		X		X		X	
Leg length		X			X		X		X		X				X				X	
Weight ¹⁰	X	X	X		X		X		X		X		X		X		X		X	
12 lead-ECG (at rest) ¹¹	X	(X)					X				X				X				X	
Safety Laboratory (blood and urine) ¹²	X ⁹	X	X	(X)	X	(X)	X	(X)	X	(X)	X	(X)	X	(X)	X	(X)	X	(X)	X	(X)
Pregnancy tests ¹³	X	X	X		X		X		X		X		X		X		X		X	
Dispense urine pregnancy test with Diary Card (if applicable) ¹³		X ¹³	X ¹³		X		X		X		X		X		X		X		X	
Review Diary Card for urine pregnancy test (if applicable) ¹³					X		X		X		X		X		X		X		X	
██████████		X			X		X		X		X									

Trial Periods	Screening	Treatment ³																		

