- Additional visits/ Phone calls (if appropriate) have to be included, in case of dose change (reduction or re-escalation) or in case of capsule’s size change. Please refer to [Section 6.2.2](#).
- Additional visits may be needed for following safety assessments: bone imaging, dental examination and dental imaging. Please refer to footnotes 21, 22, 23.
- Patients aged 21 years must complete the trial while being 21 years old. They should perform EoT visit and EoS visit (28 days after) before their 22nd birthday.

4. **For new patients**: Visit 3 applicable. For new patients in Norway, the Visit 3a is also applicable and should be performed at Week 6 (Day 43)

For roll-over patients < 26 weeks (switching from InPedILD[®] to open label extension trial before Visit 7 (week 26)): Visit 3 applicable.

[figure not shown]
For roll-over patients ≥ 26 weeks (switching from InPedILD[®] to open label extension trial at Visit 7 (week 26) or after): Visit 3 not applicable.

5. Informed consent, and assent where applicable, will be obtained before any procedure related to the study. When it is obtained before Visit 1, e.g. to allow shipment of images for central review, all Adverse Events (AEs) and Concomitant Treatments occurring/given after the informed consent (and assent where applicable) was given, have to be recorded, including those that occurred between informed consent and Visit 1. Upon obtaining informed consent, the patient/parent(s)/legal guardian will be instructed on procedures to be followed until the next study visit.

6. **For new patients who didn’t previously participate in InPedILD[®] only** - Central review of High-Resolution Computed Tomography (HRCT) for meeting inclusion criteria. One HRCT should not be older than 12 months. If the patient does not have an HRCT within 12 months of Visit 1 or the available HRCT scan fails to meet the required image acquisition specification (see image acquisition guideline in the ISF), a new HRCT can be performed at discretion of the investigator for the purposes of participation in the trial, provided the patient meets all other in-/exclusion criteria. For details about HRCT review, see [Section 3.3.2.1](#).

7. **For new patients who didn't previously participate in InPedILD® only** - Central review of previous documented biopsy for meeting inclusion criteria. For details about biopsy review, see [Section 3.3.2.1](#).

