Test results must be documented in the patient's pregnancy test diary card and will be transferred to the patient's records by site staff at the next site visit. In case of positive results, procedures defined in [Section 5.2.7.2.3](#) should be followed.

At 'a-Visits', safety blood, and urine samples will be collected and submitted to the central laboratory if needed for additional safety monitoring at the discretion of the Investigator (see cautionary notes under [Section 4.2.2.1](#) for additional safety monitoring). Safety laboratory parameters to be assessed at regular visits are listed in [Table 5.2.3:1](#) Safety laboratory parameters to be assessed at these additional visits are listed in [Table 5.2.3:2](#).

The samples may be collected at the office of a local doctor using preferably trial specific lab kits that will be sent to a central laboratory for analyses or may be analysed locally. These kits will be provided to patients at study visits as applicable. Around 2.5 mL will be taken at each a-Visit.

If laboratory values indicate abnormality, adequate and more frequent blood sampling may be performed at the discretion of the Investigator.

In case of liver function value elevations, close monitoring must be ensured by the Investigator. Refer to [Section 4.1.2](#) for monitoring elevations and [Section 3.3.4](#) for withdrawal criteria.

In case the criteria for hepatic injury are fulfilled, a number of additional measures will be performed (please see [Section 5.2.7.1](#) and the DILI Checklist provided in the eDC system). The amount of blood taken from the patient concerned will be increased due to these additional samplings.

The central laboratory will transfer the results of the analysis to the sponsor or delegate.

Table 5.2.3:1 Safety laboratory tests at scheduled site visits

The laboratory tests at regular site visits will include:

Functional lab group	Test name
Haematology	Haematocrit Haemoglobin Red blood cells (RBC) White blood cells (WBC) Platelet count Mean corpuscular volume (MCV)
Automatic WBC differential (relative and absolute)	Neutrophiles total Lymphocytes total Eosinophiles Basophiles

Functional lab group	Test name
	Monocytes Lymphocytes
Manual differential WBC (if automatic differential WBC is abnormal)	Polymorphonuclear neutrophils (segs), band neutrophils (stabs), eosinophils, basophils, monocytes, lymphocytes
Coagulation	Activated partial thromboplastin time (aPTT) Prothrombin Time (PT) INR

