7.1 NULL AND ALTERNATIVE HYPOTHESES

[figure not shown]
No confirmatory testing is performed and hence no null and alternative hypotheses are defined.

[figure not shown]

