6.7 BASELINE, TIME WINDOWS AND CALCULATED VISITS

For roll-over patients Visit 1 and Visit 2 should be conducted on the same day and should, if possible, occur the same day as the EoT Visit of the parent trial to avoid any treatment interruption. In this case, assessments conducted as part of EoT of the parent trial are not repeated for the extension trial and results are only reported in the parent trial database. Therefore, the last available result in parent trial will be considered as baseline value for the extension trial if still meeting the baseline criteria as defined in this section.

As a general rule, the last assessment/measurement observed prior to first trial drug intake will be used as baseline. If the time of the assessment/measurement was not captured, and it was on the same day on which trial medication started, it will be assumed that it was taken prior to the intake of trial medication. Similarly, if no time is reported for start of trial medication it will be assumed that all trial procedures on that day happened before trial drug intake.

Visit windowing will be performed as described in the following tables, in order to assign data to the relevant study visit based on the actual day of the assessment. Data will be

analysed using the re-assigned visits in the statistical tables. However, in the patient data listings, all visits performed will be displayed (even if outside time-window), along with the re-assigned visit.

If after windowing of visits at baseline, two or more values fall within the same baseline interval, then the last value prior to first trial drug intake will be taken into account. If after windowing of post-baseline visits, two visits fall in the same interval, then the measurement closest to the planned visit will be taken into account. If only on-treatment values are to be considered (e.g. vital signs, laboratory data), this rule will be applied to on-treatment assessments only. In case two measurements are equidistant from the planned visit, then the last one will be picked.

Table 6.7: 1 Time windowing rules for [REDACTED] vital signs (syst. and diast. blood pressure, pulse rate, weight) and laboratory tests ([REDACTED])

Time window of actual day ^[1,2]			Allocated to		
Start day	End day (included)	Length of the time-window [days]	Visit number	Visit name	Planned day of the visit
-35	1	36	2	Baseline	1
2	50	49	3	2 weeks	15
51	127	77	4	12 weeks	85
128	211	84	5	24 weeks	169
212	309	98	6	36 weeks	253

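### The week-2 laboratory and vital-sign row for Group 2 and total can mix routine Visit 3 values with selectively obtained values from roll-over patients who have no Visit 3

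*SAP*

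**What the plan says.** **Windowing.** SAP Section 6.7 re-assigns visits so as to "assign data to the relevant study visit based on the actual day of the assessment". In Table 6.7:1 the columns are start day, end day, length, visit number, visit name and planned day. The first two post-baseline rows read "2 50 49 3 2 weeks 15" and "51 127 77 4 12 weeks 85". The table covers blood pressure, pulse, weight and laboratory tests, with no exception by cohort.

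**Selection within a window.** If two post-baseline values share a window, "then the measurement closest to the planned visit will be taken into account". A tie goes to the later value. For laboratory data and vital signs only on-treatment values compete. The visible text draws no line between scheduled and unscheduled values.

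**Who has a Visit 3.** Protocol Flow Chart footnote 4 and Section 6.2.2 require it for new patients and for roll-over patients with less than 26 weeks in the parent trial. For the others the footnote says, of those switching "to open label extension trial at Visit 7 (week 26) or after): Visit 3 not applicable".

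**Where other early values come from.** On abnormal results, Protocol Section 5.2.3 says "adequate and more frequent blood sampling may be performed at the discretion of the Investigator". Section 6.2.2 adds intermediate a-visits and unscheduled visits for dose or capsule-size changes. Section 4.2.1.2 adds liver retests. An End of Treatment visit after early discontinuation can also fall in the window.

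**Display.** SAP Section 7 tabulates all Section 6.7 timepoints for Group 1 (initiated nintedanib), Group 2 (continued nintedanib) and total.

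**The concern.** A reader takes the 2-week row as the patients' state two weeks after entering this trial. For a roll-over patient without Visit 3, a value reaches that row only if someone had a reason to bring the patient in or draw blood. Patients who were well contribute nothing, so the chance of being in the row depends on clinical course. The N printed in the table shows how many patients are in it, but not that some were selected this way.

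The trial is uncontrolled and its main objective is long-term safety. The by-visit tables are therefore one of the places where a reader looks for an early change in liver enzymes. A few values drawn because of an elevation, or drawn after the dose was cut in response to one, could distort that row in either direction.

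**Working it through.** **1. Reproduce the plan's windows.** Each window in Table 6.7:1 ends midway between consecutive planned days.
- Visit 3: (15 + 85)/2 = 50. Days 2 to 50, length 50 − 2 + 1 = 49.
- Visit 4: (85 + 169)/2 = 127. Days 51 to 127, length 77.

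With the last window ending at planned day + 42, all 13 post-baseline windows and lengths reproduce exactly. The table is internally correct.

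**2. Compare routine attendance with the window.** The Flow Chart allows ±3 days for Visits 3 and 4.
- Visit 3: days 12 to 18, of which 7 fall in days 2 to 50.
- Visit 4: days 82 to 88, of which 0 fall in days 2 to 50.

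No routine visit of a roll-over patient with 26 weeks or more can supply a week-2 value.

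**3. Which column these patients enter.** Protocol Section 1.1 gives Part A of the parent trial as 24 weeks. A roll-over patient with 26 weeks or more has therefore entered Part B and belongs to Group 2. Group 2 also holds nintedanib patients who rolled over before week 26 and do have a Visit 3. The Group 2 row is a mixture, and the total adds the Group 1 values.

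**4. Possible share of non-routine values in the Group 2 row.** The documents give only at least 30 expected roll-over patients, not the split at 26 weeks, so the following inputs are assumptions. Let s be the fraction of Group 2 with 26 weeks or more, and u the fraction of those with an early value. Assume complete Visit 3 data in the rest. Then

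share = s·u / (s·u + 1 − s).

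| s | u = 0.1 | u = 0.5 |
|---|---|---|
| 0.5 | 0.05/0.55 = 9% | 0.25/0.75 = 33% |
| 0.7 | 0.07/0.37 = 19% | 0.35/0.65 = 54% |
| 0.9 | 0.09/0.19 = 47% | 0.45/0.55 = 82% |
| 1.0 | 100% | 100% |

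**5. Retests in other windows.** Section 4.2.1.2 calls for a retest after 48 to 72 hours.
- Visit 4 on day 82: a retest on day 84 or 85 is nearer to day 85 and replaces the scheduled value.
- Visit 4 on day 83: a retest on day 85 or 86 also replaces it.
- Visit 4 on day 84: a retest on day 86 ties, and the later value is taken.

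The route is real but narrow.

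**6. Which parameters.** The a-visit panel (Protocol Table 5.2.3:2) holds liver enzymes, bilirubin, creatinine, total protein, electrolytes and urinalysis. It has no vital signs, weight, haematology or coagulation. Early vital signs from these patients can come only from dose-change or capsule-size visits or an early End of Treatment visit, and Section 4.1.4 lets some dose changes be handled by telephone.

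**The case against.** A reader might infer that the week-2 row of the continuing patients consists wholly of samples taken because something was wrong. The documents do not support that, for two reasons.
- Roll-over patients with 26 weeks or more have no row of their own. The Group 2 row is purely non-routine only if every Group 2 patient had 26 weeks or more, which is not stated.
- Not every unscheduled value signals a problem. Capsule-size changes, dose increases after recovery and laboratory tests recommended by the Safety Monitoring Committee need not, and an early End of Treatment visit is defined by the protocol.

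A reader might also infer a large distortion from a constructed example. Suppose no Group 2 patient has a Visit 3, 3 of 30 have a value at 4 × ULN, 27 are unsampled at 0.6 × ULN, and 25 Group 1 patients are at 0.6 × ULN. The tabulated total mean is (25 × 0.6 + 3 × 4)/28 = 0.96. The like-for-like mean over all 55 is (25 × 0.6 + 3 × 4 + 27 × 0.6)/55 = 0.79. The median of the total is 0.6 either way, and SAP Section 7 prefers medians and quartiles where some data are extreme. This example is also an extreme case, because it assumes away every routine Group 2 value.

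The strongest objection is about consequence. "No confirmatory testing is performed and hence no null and alternative hypotheses are defined", listings show every visit performed, and liver safety rests on worst values, time to first elevation, hepatic-injury criteria and individual profiles. Laboratory analysis also follows a sponsor standard that is not in the documents, and the table title is partly redacted, so a rule on unscheduled values may exist elsewhere.

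All of this stands and limits the point. It does not remove it: as written, the SAP puts non-routine values under a label for a visit that these patients do not have.

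**Conclusion.** The point holds in limited form. In the Group 2 and total columns of the by-visit laboratory and vital-sign tables, the week-2 row can mix routine Visit 3 values with selectively obtained values from patients who have no Visit 3. Its size cannot be computed: the 9% to 100% range above rests entirely on assumed splits and sampling rates. The effect is confined to descriptive by-visit summaries and is weaker for vital signs than for liver enzymes. The incidence of treatment-emergent adverse events and the worst-value and time-to-event liver outputs do not use these windows. The verdict assumes that no unseen sponsor standard already separates scheduled from unscheduled values. This is a cheap improvement to a safety display, not a threat to the trial's conclusions.

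**What to change.** In SAP Section 6.7:
- Restrict the Visit 3 row of Table 6.7:1 to patients for whom Visit 3 is planned, that is, new patients (including those handled as new) and roll-over patients with less than 26 weeks in the parent trial.
- For the other roll-over patients, do not allocate values on days 2 to 50 to a 2-week row. Keep those values in the worst-value, time-to-event and listing outputs.
- Where a scheduled and an unscheduled value share a window, take the scheduled one.

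A scheduled-only filter for every by-visit table is not needed. Nor should the Visit 4 window simply be stretched back to day 2 for these patients. Table 6.7:2 does that for height because height is not planned at Visit 3 for anyone. Here it would let an early unscheduled value stand for week 12 whenever Visit 4 is missing.

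The cost is one derivation flag and a few sentences. A few early unscheduled or End of Treatment values no longer enter the by-visit means. If the sponsor's laboratory standard already does this, a sentence in the SAP saying so, and extending it to vital signs and weight, is enough.

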7. PLANNED ANALYSIS

Unless otherwise specified, all analyses described in this section will be done on the Treated Set. All available data (i.e. data for all available timepoints, as defined in [Section 6.7](#)) will be presented in the summary tables, irrespective if the timepoint is specified in the endpoint definition in the CTP. For endpoints with time intervals, only data for the intervals specified in the endpoint definition will be presented.

The labelling and display format of statistical parameters will follow BI standards (9). For End-Of-Text tables, the set of summary statistics is: N / Mean / SD / Min / Median / Max.

In descriptive statistics tables, mean, SD and median will be rounded to one additional digit than the raw individual value. For tables that are provided for endpoints with some extreme data, median, quartiles and percentiles should be preferred to mean, standard deviation, minimum and maximum.

Tabulations of frequencies for categorical data will include all possible categories and will display the number of observations in a category as well as the percentage (%) relative to the respective group (unless otherwise specified, all patients in the respective patient set whether they have non-missing values or not). The precision for percentages should be one decimal point. The category missing will be displayed only if there are actually missing values.

Unless otherwise specified, all analyses will be provided by patient group (initiated nintedanib or continued nintedanib) and overall (total):

[figure not shown]
- Group 1: Initiated nintedanib
 - New patients
 - Patients who prematurely discontinued treatment permanently in 1199-0337
 - Completed patients from 1199-0337 not able to roll over into the extension trial within 12 weeks following their End of Treatment visit in the parent trial (i.e. time period between last dose of trial drug in parent trial and first dose in extension trial is greater than 12 weeks)
 - Patients from 1199-0337 placebo arm Part A (i.e. from double-blind placebo arm who did not enter the open-label nintedanib period and only received placebo in the parent trial)
- Group 2: Continued nintedanib
 - Patients from 1199-0337 Part B (i.e. from open-label nintedanib period of the parent trial, time period between last dose of trial drug in parent trial and first dose in extension trial is less than or equal to 12 weeks)
 - Patients from 1199-0337 nintedanib arm Part A (i.e. from double-blind nintedanib arm of the parent trial, time period between last dose of trial drug in parent trial and first dose in extension trial is less than or equal to 12 weeks)

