For all patients, during treatment period, dose is adjusted based on patient's weight. Dose reduction to the next lower dose is possible to manage adverse events. The lowest possible dose is 25 mg b.i.d. (50 mg daily).

Roll-over patients will be requested to stay in the trial for at least 156 weeks (until Visit 15). At week 156, roll-over patients who can be treated with nintedanib or alternative treatment options outside the clinical trial will have their EoT Visit instead of Visit 15.

The remaining roll-over patients will continue in the trial until nintedanib or alternative treatment options can be made available to them outside the clinical trial.

New patients will be requested to stay in the trial until the end of trial (with expected minimum treatment duration of 76 weeks), then patients will perform their EoT Visit and enter in the 28-days follow-up period off-treatment until End of Study Visit (EOS).

Exception: patients aged 21 years must complete the trial before their 22nd birthday. Consequently, a treatment duration of at least 3 years might not be reached by some patients aged 21.

Patients completing trial while being 21 years old, even with a treatment duration less than 3 years, will be considered as completed patients.

The overall end of trial will take place approximately when last roll-over patient is expected to reach 3 years of treatment () ensuring nintedanib or alternative treatment options (e.g., via marketing authorization, via compassionate use, or via similar process) will be available for all remaining patients (roll-over or new patients) outside the trial at this time.

At this time, all the remaining patients will perform their EoT Visit. For logistical reasons, it may be planned that EoT visit of all remaining patients will occur within 6 weeks before the planned date of Visit 15 of last roll-over patient. If regular scheduled visit is planned for a patient during this period of 6 weeks, then the patient will skip this regular visit and will perform directly the EoT visit instead. After the EoT visit, all remaining patients will enter a 4-week follow-up period.

Trial medication will be stopped prematurely if a reason for withdrawal is met (refer to [section 3.3.4](#)).

Roll-over patients will be considered as prematurely discontinued from trial treatment if they stop trial medication before week 156 (except at the age of 21).

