- Dental examination: Previous panoramic x-ray within 12 weeks prior Visit 2 should be used as baseline. If a previous dental examination as outlined above is not available, a dental examination will be conducted according to protocol requirements (see [Section 5.2.6](#)) and evaluated at site.
- Dental imaging: Previous panoramic x-ray within 24 weeks prior Visit 2 should be used as baseline. If a dental imaging is not available as outlined above, a dental imaging will be conducted according to protocol requirements (see [Section 5.2.6](#)). The panoramic x-ray will be sent to central evaluation by a paediatric dentistry expert in a timely manner.

Visits 3, 4, 5, 6, 7, 8, 9, 10, 11, 12, 13, 14, 15, X (treatment period)

Additional clinic visits will be scheduled on regular basis from Visit 2 until End of Treatment (EOT) visit. Detailed procedures and assessment to be performed at each Visit are described in [Flow Chart](#) and [Section 5](#).

As the treatment duration for each patient will be variable, some visits may not apply (to some new patients and to some patients aged 21)

For roll-over patients with 26 weeks or more in InPedILD[®], Visit 3 is not needed. This additional visit is scheduled after 2 weeks of treatment to assure close monitoring of new patients and roll-over patients with less than 26 weeks in InPedILD[®], during the first month of study.

The following must be ensured during trial visits according to the study [Flow Chart](#):

[figure not shown]
- [REDACTED]

- FVC measurements at all visits should be performed approximately at the same time of the day to reference time point at Visit 2.

Observations and procedures:

Observations and procedures [redacted]:

Other observations and procedures:

- Compliance will be checked, and drug accountability will be completed.
- Criteria for dose reduction / interruption will be checked, if any.

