310	407	98	7	52 weeks	365
408	491	84	8	64 weeks	449
492	575	84	9	76 weeks	533
576	673	98	10	88 weeks	617
674	771	98	11	104 weeks	729
772	855	84	12	116 weeks	813
856	939	84	13	128 weeks	897
940	1037	98	14	140 weeks	981
1038	1135	98	15	156 weeks	1093

^[1] First trial drug intake date is taken into account as reference to calculate time windows.

^[2] For analyses of LDH as biomarker, values are only considered up to + 7 days after last trial drug intake.

Table 6.7: 2 Time windowing rules for height and body mass index

[figure not shown]
Time window of actual day ^[1]			Allocated to		
Start day	End day (included)	Length of the time-window [days]	Visit number	Visit name	Planned day of the visit
-35	1	36	2	Baseline	1
2	127	126	4	12 weeks	85
128	211	84	5	24 weeks	169
212	309	98	6	36 weeks	253
310	407	98	7)	52 weeks	365
408	491	84	8	64 weeks	449
492	575	84	9	76 weeks	533
576	673	98	10	88 weeks	617
674	771	98	11	104 weeks	729
772	855	84	12	116 weeks	813
856	939	84	13	128 weeks	897
940	1037	98	14	140 weeks	981
1038	1135	98	15	156 weeks	1093

[figure not shown]
^[1] First trial drug intake date is taken into account as reference to calculate time windows.

[figure not shown]
Table 6.7: 3 Time windowing rules for leg length

[figure not shown]
Time window of actual day ^[1]			Allocated to		
Start day	End day (included)	Length of the time-window [days]	Visit number	Visit name	Planned day of the visit
-35	1	36	2	Baseline	1
2	127	126	4	12 weeks	85
128	211	84	5	24 weeks	169
212	309	98	6	36 weeks	253
310	449	140	7	52 weeks	365
450	631	182	9	76 weeks	533
632	813	182	11	104 weeks	729
814	995	182	13	128 weeks	897
996	1177	182	15	156 weeks	1093

^[1] First trial drug intake date is taken into account as reference to calculate time windows.

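### By-visit tables for laboratory, vital signs, weight, height and BMI stop at day 1135, although the same assessments continue every 12 weeks after week 156

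*SAP*

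**What the plan says.** **Schedule.** The protocol Flow Chart (V12 to end of study) places Visit X every 12 weeks after week 156, that is, at day 1093 plus multiples of 84 days, within 7 days either way. Vital signs, weight, standing and sitting height and safety laboratory are taken at each Visit X and at end of treatment (EoT).

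**Who is still there.** Roll-over patients with access to nintedanib or an alternative outside the trial have EoT at week 156. For the others, protocol Section 3.1 says: "The remaining roll-over patients will continue in the trial until nintedanib or alternative treatment options can be made available to them outside the clinical trial". On closing the trial it says: "The overall end of trial will take place approximately when last roll-over patient is expected to reach 3 years of treatment".

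**Windows.** In SAP Section 6.7 the last row of both Table 6.7:1 and Table 6.7:2 is "1038 1135 98 15 156 weeks 1093" (start day, end day, length, visit, week, planned day). For leg length (Table 6.7:3) it is "996 1177 182 15 156 weeks 1093".

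**Use of the windows.** Section 6.7 has the statistical tables use the re-assigned visits; visits outside a window are promised only for the patient listings. Section 7 then describes the content of the summary tables as "All available data (i.e. data for all available timepoints, as defined in" Section 6.7). Section 7.8.2.1 wants laboratory results shown over the whole trial and points to Table 6.7:1.

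**The concern.** The trial's main objective is long-term safety and tolerability, and protocol Table 1.4.2:1 names maturation and growth as a paediatric risk to be monitored partly through height. A by-visit table of height, BMI, weight, blood pressure or laboratory values is where a reader looks for drift over time. If it ends at week 156 while patients are still being measured, the part left out is the longest exposure, from assessments already made in children.

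The SAP also seems to pull two ways. Its exposure categories in Section 5.4.3 include one above 156 weeks, and its on-treatment period in Section 7.8 runs to last intake plus 28 days with no cap at week 156. Section 7 speaks of all available data. The visit windows do not follow.

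**Working it through.** **1. Reproduce the SAP's window ends.** Each post-baseline window ends at the midpoint between consecutive planned days.
- Visit 14, Tables 6.7:1 and 6.7:2: (981 + 1093)/2 = 1037, as printed.
- Visit 15, same tables: (1093 + 1177)/2 = 1135, as printed. Length 1135 − 1038 + 1 = 98, as printed.
- Visit 15, leg length: (1093 + 1261)/2 = 1177, as printed.

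All other post-baseline rows of the three tables reproduce in the same way. The Visit 15 end of day 1135 is what the rule gives only if a visit on day 1177 (week 168) follows. That visit has no row.

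**2. Compare Visit X with the last window.** Planned day = 1093 + 84k, ±7 days.

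| k | Week | Planned day | Allowed days | In Table 6.7:1 or 6.7:2? |
|---|---|---|---|---|
| 1 | 168 | 1177 | 1170–1184 | no |
| 2 | 180 | 1261 | 1254–1268 | no |
| 3 | 192 | 1345 | 1338–1352 | no |
| 4 | 204 | 1429 | 1422–1436 | no |

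Day 1135 is week (1135 − 1)/7 = 162, or 6 weeks after week 156. Every Visit X, and any EoT visit after day 1135, has no window.

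**3. Who is affected.**
- New patients: protocol Section 3.1 gives a stay "with expected minimum treatment duration of 76 weeks", and Section 3.3 an estimated 18 months of recruitment. The longest planned stay is about 76 + 18 × 30.4375/7 = 154 weeks, so on these figures few or none pass week 156.
- Roll-over patients who stop treatment early complete the trial at week 156 and contribute no Visit X. Later values are therefore essentially on treatment.
- The gap falls mainly on roll-over patients who remain on drug after week 156.

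**4. How many assessments per patient.** The spread of roll-over entry dates is not in the documents. Assume a patient enters m months before the last roll-over patient and stays until that patient reaches week 156. Visit X assessments without a window = whole part of (m × 30.4375/84):

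| m (months) | 0 | 3 | 6 | 9 | 12 | 18 |
|---|---|---|---|---|---|---|
| Visit X without window | 0 | 1 | 2 | 3 | 4 | 6 |

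Under this assumption a patient has data past day 1135 if entry was more than 6 weeks before the last roll-over patient. Section 3.1 lets the closing EoT visits fall up to 6 weeks before that patient's planned Visit 15; at the full 6 weeks the lead needed is more than 12 weeks.

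**The case against.** **The values are not lost.** A reader might infer that data after day 1135 drop out of the analysis altogether. The SAP does not support that. Listings show every visit, in or out of window. The primary adverse-event analysis and the incidence rates, the worst-value liver and hepatic-injury summaries, time to liver enzyme elevation, individual liver time courses, minimum relative weight change and exposure are not built on these windows. Laboratory summaries against reference ranges follow a sponsor standard that cannot be seen here. This part of the objection stands and limits the point to by-visit summaries.

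**Growth is only partly touched.** Sitting height and leg length are listed only (SAP Section 7.8.3), so their windows change no table. Growth-plate and dental findings are reported as adverse events. Only standing height and BMI are concerned. This stands.

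**The number of patients.** A reader might infer that most of the expected 30 or more roll-over patients are affected. With 30 entering evenly over 26 or 52 weeks, 30 × (26 − 6)/26 = 23 or 30 × (52 − 6)/52 = 26 would have later data. The documents give neither spread. Closing EoT visits 6 weeks earlier reduces the counts to 30 × (26 − 12)/26 = 16 and 30 × (52 − 12)/52 = 23. Leaving at week 156 with outside access, early discontinuation and exit before the 22nd birthday reduce them further. No count should be quoted.

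**The cut may be deliberate, or a rule may be hidden.** Week 156 is the minimum period for roll-over patients, version 2.0 of the SAP was revised for the prolongation, and parts of Section 6.7 are redacted. But no visible text states a cut, the footnotes follow directly after each Visit 15 row, and the last window is cut as if a further visit followed. Neither suggestion can be ruled out, and neither is documented.

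**Conclusion.** The point holds for by-visit summaries of blood pressure, pulse, weight, laboratory tests, height and BMI. On the visible text, on-treatment values after day 1135 have no visit to which they can be assigned and so do not appear in those tables, although Section 7 says all available data will be shown. The primary endpoint and the analyses that do not use visit windows are unaffected.

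The size in patients cannot be derived: the entry spread is not given and the end-of-trial date is redacted. It is zero only if no roll-over patient is assessed more than 6 weeks after week 156. Variables whose names or windows are redacted in Section 6.7 were not assessed. This is a minor gap, worth closing because the values omitted are those at the longest exposure.

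**What to change.** Add rows to Tables 6.7:1 and 6.7:2 by the existing midpoint rule:
- week 168, planned day 1177: days 1136–1219, since (1177 + 1261)/2 = 1219;
- week 180, planned day 1261: days 1220–1303, since (1261 + 1345)/2 = 1303;
- then a further 84-day window for each later Visit X.

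The leg-length table needs no change for the summaries. If by-visit tables are meant to stop at week 156, state that and correct the Section 7 wording, so that a reader knows later values are in the listings and in the analyses that do not use visit windows.

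The cost is a few rows in two SAP tables, with no new data collection. The drawback is that late columns may be sparse, especially by patient group, and should be read with their n.
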